Based on clinical experience to date in myelofibrosis, the following adverse effects may be associated with ruxolitinib: thrombocytopenia, anemia, neutropenia, bruising dizziness, headache, urinary tract infection, weight gain, flatulence, and herpes zoster. Thrombocytopenia, anemia, and neutropenia are dose-related effects, which occur at a median of 8 weeks after initiation of ruxolitinib, and in studies of longer duration have been generally treated by withholding ruxolitinib. Occasionally patients with anemia may require a transfusion. Patients taking ruxolitinib may be at risk for infection and should be monitored for this. The incidence of clinically significant hematologic toxicity is expected to be very low in the current study population, due to the short ruxolitinib exposure, as well as the absence of a primary bone marrow malignancy predisposing to hematologic toxicity.

Some people who take ruxolitinib have developed certain types of non-melanoma skin cancers.

Availability

All tablets are oval and white with "INCY" on one side and "25" on the other. Additional information regarding ruxolitinib can be found in the package insert.

Storage and handling

Phase 2 - Ruxolitinib Page 29 of 67

In addition to the active ingredient, each ruxolitinib tablet contains microcrystalline cellulose, lactose monohydrate, magnesium stearate, colloidal silicone dioxide, sodium starch glycolate, povidone, and hydroxypropyl cellulose. Ruxolitinib will be supplied as 5 mg tablets in bottles containing 60 tablets each. Labels contain, at a minimum, the following information: product name, tablet strength, batch number, directions for use, storage conditions, and appropriate caution statements. Ruxolitinib tablets should be stored in a secure area at 25°C (77°F); excursions permitted between 15°-30°C (59°-86°F).

Side Effects

Complete and updated adverse event information is available in the Investigational Drug Brochure and/or product package insert.

4.2 **Drug Accountability**

The Investigational Pharmacist will manage drug accountability records. Damaged supplies will be destroyed at the study site and adequate records of the damaged supplies will be kept at the site. Study investigators will be responsible for drug accountability.

4.3 **Drug Ordering**

Ruxolitinib will be supplied by Incyte Pharmaceuticals.

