- If participants experience any grade 3-4 ruxolitinib-related non-hematologic toxicities in the neo-adjuvant window, the study drug will be discontinued and they will be removed from the study. (Exception: Patients with asymptomatic grade 3 electrolyte abnormalities manageable with repletion) Patients may also be removed from study for intolerable non-hematologic toxicities of any grade, which persist despite optimal medical management.
- If participants experience grade ≥ 3 thrombocytopenia or neutropenia, ruxolitinib will be discontinued and they will be removed from the study.
- Grade 3 anemia does not require discontinuation from protocol. Patients may be transfused per discretion of the treating physicians.
- For mild or moderate (grade 1 or 2) side effects that are difficult to tolerate, treatment
 may be held for up to 1 week. Treatment may be resumed at the same dose, if there is
 improvement by at least one grade. Dose delays more than 1 week will not be permitted.
 If treatment is restarted, study physicians should aim for at least 3 days of ruxolitinib
 exposure prior to planned surgery.

In two Phase 3 clinical studies of ruxolitinib in myelofibrosis, the median time to onset of first CTCAE grade two or higher anemia was 6 weeks, and approximately 8 weeks until onset of grade 3 or 4 thrombocytopenia. In nearly all cases, ruxolitinib-induced anemia and thrombocytopenia could be reversed with dose reduction or interruption; occasionally red blood cell or platelet transfusions were required. Thus, given the short 2-3 weeks of treatment during this study, it is expected that few, if any, participants will develop hematologic abnormalities. Moreover, participants in the current study do not have a primary bone marrow malignancy which is the target of ruxolitinib and thus predisposes to hematologic toxicity. Any participants that experience anemia or thrombocytopenia may be transfused if deemed necessary by the treating physician.

Although clinically significant hematologic and non-hematologic toxicity is unexpected during the 14-21 days of protocol treatment in patients with operable HNSCC, a continuous monitoring rule for excess toxicity will be instituted. Please see Section 5.6 below.

5.6 **Monitoring and Toxicity Management**

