8.2.3 Safety Lead-in

A continuous monitoring rule for safety will be instituted, to guard against excess toxicity from pre-operative treatment with ruxolitinib at the FDA-indicated starting dose for patients with myelofibrosis (20 mg bid for patients with a platelet count \geq 200,000 or 15 mg bid for patients with a platelet count \geq 150,000 and < 200,000). The first cohort of 6 patients will be treated at this starting dose. After enrollment of the 6th patient, we will continuously monitor the number of

Phase 2 - Ruxolitinib Page 49 of 67

patients who discontinue ruxolitinib and come off study for ruxolitinib-attributable toxicity. A qualifying toxicity must be at least possibly related to ruxolitinib, as judged by the treating investigator, and fulfill one of the following definitions:

- Grade ≥ 3 non-hematologic toxicity, with the exception of asymptomatic electrolyte abnormalities manageable with repletion.
- Intolerable non-hematologic toxicities of any grade, which persist despite optimal medical management.
- Grade ≥ 3 thrombocytopenia or neutropenia.

If the posterior probability of \geq 33% toxicity rate exceeds 50% for patients having to discontinue window treatment due to qualifying toxicity, this would be considered unacceptable and would result in de-escalating the starting dose of ruxolitinib to 10 mg p.o. bid, the FDA-indicated starting dose in polycythemia vera, for all subsequent patients. This would be the starting dose in all patients with a qualifying platelet count for this study (\geq 150,000), including those with platelet count \geq 150,000 and < 200,000 and those with platelet count > 200,000. (see section 5.2 Dose De-Escalation Rule)

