3.3 Review of Adverse Event Rates

If an increase in the frequency of Grade 3 or 4 adverse events (above the rate reported in the Investigator Brochure or package insert) is noted in the study, the Study Chair at the UCSF Coordinating Center is responsible for notifying the DSMC at the time the increased rate is identified. The report will indicate if the incidence of adverse events observed in the study is above the range stated in the Investigator Brochure or package insert.

Phase 2 - Ruxolitinib Page 62 of 67

If at any time the Study Chair stops enrollment or stops the study due to safety issues, the DSMC Chair and DSMC Director must be notified within 1 business day and the IRB must be notified within 10 business days via an iRIS Reporting Form.

Data and Safety Monitoring Committee Contacts:

[name]

UCSF HDFCCC

[name]

DSMC Monitors

UCSF HDFCCC

[name]

Revision #3 (12Nov2017)

Approved by NCI (09Feb2012)

Phase 2 - Ruxolitinib Page 63 of 67

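### Sections 5.5 and 8.2.3 set different electrolyte exceptions, so a patient removed for a related grade 4 abnormality is left out of the de-escalation count; stops for grade 4 anemia are also unplaced

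*Combined protocol and SAP*

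**What the plan says.** Two lists govern toxicity during the treatment window.

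**Removal list (protocol 5.5, Dose Modifications and Dosing Delays).** "If participants experience any grade 3-4 ruxolitinib-related non-hematologic toxicities in the neo-adjuvant window, the study drug will be discontinued" and the patient leaves the study. The carve-out reads "Exception: Patients with asymptomatic grade 3 electrolyte abnormalities manageable with repletion". Grade 3 or higher thrombocytopenia or neutropenia also means removal. On anemia the section says "Grade 3 anemia does not require discontinuation from protocol" and does not mention grade 4. Section 3.4 separately lets the investigator end treatment for any adverse event or laboratory abnormality when continuing is judged not to be in the participant's interest.

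**Counting list (8.2.3, Safety Lead-in).** From the sixth patient on, the plan tracks patients who stop ruxolitinib and come off study for toxicity at least possibly related to the drug. To qualify, the toxicity must be one of three kinds: "Grade ≥ 3 non-hematologic toxicity, with the exception of asymptomatic electrolyte abnormalities manageable with repletion"; intolerable non-hematologic toxicity of any grade despite optimal management; or "Grade ≥ 3 thrombocytopenia or neutropenia". Anemia is not listed at any grade.

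The count feeds the Table 5.2 rule in section 5.2. The starting dose is lowered when the posterior probability that the discontinuation rate exceeds 33% is itself above 50%, under a Beta(1, 9) prior. The column of counts in that table is labelled as treatment-related discontinuations, and the footnote defines the monitored quantity as the discontinuation rate.

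**The concern.** A rule that monitors discontinuations should count the patients whom the protocol itself discontinues. Here the carve-out from removal and the carve-out from counting differ by one grade qualifier, so the protocol can require a removal that the rule then ignores. Two people working in good faith, one from Table 5.2 and one from the 8.2.3 definitions, would report different counts for the same patients. Anemia leaves a smaller gap of the same kind: a drug stop is possible, but no text says whether it counts.

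This is the trial's only de-escalation rule, and a count that is too low can only delay or prevent the dose change it is meant to trigger.

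**Working it through.** **1. The lists side by side (events related to ruxolitinib)**

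| Event | Removal under 5.5 | Counted under 8.2.3 | Agree? |
|---|---|---|---|
| Asymptomatic, repletable electrolyte abnormality, grade 3 | Not required | No | Yes |
| The same, grade 4 | Required | No | **No** |
| Other non-hematologic, grade 3 or higher | Required (5.5 says grade 3-4) | Yes | Yes |
| Thrombocytopenia or neutropenia, grade 3 or higher | Required | Yes | Yes |
| Anemia, grade 3 | Not required | No | Yes |
| Anemia, grade 4 | Not stated | No | Unclear |
| Anemia, discretionary stop under 3.4 | Allowed | No | Stop not counted |

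The clause in 8.2.3 on intolerable toxicity of any grade does not close the second row, because an asymptomatic abnormality is not naturally described as intolerable. It does not reach anemia either, because it is limited to non-hematologic events.

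**2. Reproducing Table 5.2**

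Inputs from section 5.2: prior Beta(1, 9), rate limit 0.33. With r counted discontinuations among n patients the posterior is Beta(1 + r, 9 + n − r), and the tabulated quantity is its upper tail beyond 0.33. For 5 of 6 this is P(Beta(6, 10) > 0.33) = .629, as printed. All ten rows match to three decimals, as do the binomial tail probabilities in the last column.

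**3. Effect of one uncounted removal at a boundary**

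The count becomes r − 1 and the posterior becomes Beta(r, 10 + n − r). For 4 of 6: P(Beta(5, 11) > 0.33) = .415.

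| n | Boundary r | Posterior at r | Posterior at r − 1 |
|---|---|---|---|
| 6 | 5 | .629 | .415 |
| 8 | 6 | .685 | .489 |
| 11 | 7 | .673 | .492 |
| 14 | 8 | .664 | .494 |
| 17 | 9 | .657 | .496 |
| 20 | 10 | .650 | .498 |
| 23 | 11 | .645 | .4997 |
| 27 | 12 | .594 | .454 |
| 30 | 13 | .592 | .458 |
| 33 | 14 | .590 | .460 |

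Every value in the last column is below .50, so the rule would not fire. This holds by construction, because each tabulated r is the smallest count that triggers. The table shows what happens when the missed event is the deciding one. It says nothing about how often that occurs.

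**4. Sensitivity to the share missed (assumed; the documents give no share)**

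The same posterior rule is checked after every patient from the 6th to the 45th, by exact recursion. The true stop rates and the shares missed are illustrative.

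| True stop rate | None missed | 10% missed | 20% missed | 30% missed |
|---|---|---|---|---|
| 40% | .740 | .554 | .354 | .186 |
| 50% | .971 | .898 | .740 | .504 |

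The entries are probabilities of triggering by 45 patients. They show the direction and steepness of the effect. They do not estimate what will happen in this trial.

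**The case against.** The strongest reply is that the electrolyte case is narrow. The abnormality must be grade 4, asymptomatic, repletable and drug-related, and it must also be the deciding event at a boundary. After screening, chemistries are scheduled once before surgery, within 5 days of it, so such a finding would usually surface when drug is about to end anyway. This stands, and it limits the practical size. It does not remove the contradiction between the two sections.

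A reader might infer more in three ways that the documents do not support.

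- *That the lists conflict on anemia generally.* They do not. Grade 3 anemia is neither a required removal nor a counted event. The gap is confined to grade 4, on which 5.5 is silent, and to discretionary stops under 3.4.
- *That the adverse-event rate alert in Appendix 2, section 3.3 is set at myelofibrosis rates and so could hardly fire for anemia.* The text refers only to frequencies "above the rate reported in the Investigator Brochure or package insert". It names no population and no test. The hematology rates in Table 5.6 come from a myelofibrosis study, but taking them as the alert's reference is an assumption.
- *That severe anemia would otherwise go unseen.* Section 7.6 has the Site Committee review adverse events weekly and grade 3-5 events monthly, and serious suspected reactions go to the DSMC. Appendix 2, section 3.2 requires serious events to reach the Coordinating Center within 1 business day. A blood count is scheduled within 5 days before surgery. These routes work case by case and do not repair the count, but they answer any claim that oversight is absent.

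**Conclusion.** The concern holds in a limited form. Sections 5.5 and 8.2.3 contradict each other on asymptomatic, repletable grade 4 electrolyte abnormalities: removal is mandatory, yet the removal is excluded from a rule that is described as counting treatment-related discontinuations. The handling of a stop for grade 4 anemia, or of a discretionary anemia stop, is undefined in the removal list and uncounted in the other.

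The statistical machinery of Table 5.2 is sound; what is at issue is which events enter it. One missed event changes the decision only at a boundary, for example .415 instead of .629 at six patients. How often that would happen cannot be derived from the documents. It is probably rare, and section 4.1.1 itself says of blood toxicity that "The incidence of clinically significant hematologic toxicity is expected to be very low in the current study population". The point is worth correcting because the rule should count what it says it counts, not because a large effect has been shown.

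**What to change.** In the next amendment:

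1. Reconcile 5.5 and 8.2.3 to one electrolyte exception, with the same grade limit in both places.
2. State in both sections how grade 4 anemia is handled, for removal and for counting.
3. Define the Table 5.2 count as every discontinuation for toxicity at least possibly related to ruxolitinib under that single list, and say explicitly whether a discretionary stop under 3.4 for related toxicity is included.

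Which grades lead to removal is a clinical decision for the sponsor; the statistical requirement is only that the two sections agree. The boundaries in Table 5.2 need no recalculation. The cost is a few words in two sections, plus a check of any patients already enrolled against the unified definition.

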8.2.4 Accrual Estimates

Accrual of 2 evaluable patients per month is expected for total enrollment period of approximately 12 months.

8.3 Interim Analyses and Stopping Rules

This is an open label biomarkers study. No interim analysis is planned.

8.4 **Analyses Plans**

8.4.1 **Analysis Populations**

Safety Population

The safety population will include all enrolled patients who receive at least one dose of ruxolitinib and have the potential to complete pharmacodynamics biomarkers assessments at baseline and the end of study treatment window. Although the risk from specimen collections for biomarker assessment is limited and low, all patients will be evaluable for toxicity and safety assessment of ruxolitinib. Patients who are determined ineligible after enrollment or who are not evaluable for safety analysis (e.g. due to withdrawal of consent or failure of specimens collection as not related to tumor progression and not treatment-related toxicity) will be replaced (see section 8.2.2 for details).

Efficacy Population

The efficacy population for the primary endpoint of 35% or greater reduction in tumor size will include all enrolled patients who have measurable disease present at baseline and have completed tumor assessment at the end of study window. Patients who are determined ineligible after enrollment or who are not evaluable for safety analysis (e.g. due to withdrawal of consent or failure of specimens collection as not related to tumor progression and not treatment-related toxicity) will be replaced (see section 8.2.2 for details).

Phase 2 - Ruxolitinib Page 50 of 67

Version date: 03-22-2023 Protocol CC# 16201

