1.4.2 Additional Analysis

To determine if expression of serum proteins or DNA polymorphisms predict response to ruxolitinib targeting, paired serum (baseline, post-treatment) and baseline peripheral blood mononuclear cells (PBMCs) will be isolated. Blood will be processed for serum and isolation of PBMCs. Serum will be analyzed for proteomic markers using mass spectroscopy and luminex ELISA assays. DNA will be isolated from PBMC samples for SNP analysis. Tissue will be processed for DNA, fluorescence in situ hybridization (FISH), tissue microarrays, and

Phase 2 - Ruxolitinib Page 22 of 67

immunohistochemistry microarrays. Both uniplex and multiplex serum cytokine profile analysis, for correlation with other biomarkers and clinical responsiveness will be performed. For specific cytokines of interest, including IL-6, ELISA kits will be used. For multiplex analysis, the technology developed by Luminex Corporation (Austin, TX, http://www.luminexcorp.com) will be used. It enables a laboratory to simultaneously measure up to 100 analytes in a single microplate well, using very small sample volumes (less than 50 microliters). Previous studies have shown that a multi-marker panel offering the highest diagnostic power was comprised of 22 biomarkers, including EGF, EGFR, Cyfra 21-1, AFP, IL-8, MMP-3, CA 72-4, CA 15-3, MMP-2, TNF-RI, IL-7, HCGb, MIF, Mesothelin, MCP-1, IL-1Ra, FGFb, CEA, sVCAM-1, tPAI 1, RANTES, IGFBP-1. Statistical analysis using our novel ADE algorithm resulted in a sensitivity of 84.5%, specificity of 98%, and 92% of patients with active head and neck cancer correctly classified from a cross-validation serum set³⁶. Further proteomic analysis will be performed using IHC microarrays.

2 Objectives of the Study

2.1 **Primary Objective**

To identify baseline and/or pharmacodynamic biomarkers of response to ruxolitinib based upon association with quantitative change in tumor size (ΔTumor size) following 14-21 days of neoadjuvant ruxolitinib in patients with operable HNSCC. We hypothesize that ΔTumor size will correlate with five prioritized, predictive biomarkers which will be designated for specialized alpha spending: 1) baseline expression of pSTAT3; 2) change in expression of pSTAT3; 3) change in expression of the STAT3 target gene cyclin D1; 4) baseline silencing of protein tyrosine phosphatase receptors D or T (PTPRD or PTPRT) by mutation or methylation; 5) baseline elevation in peripheral inflammatory markers (C-reactive protein [CRP]).

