2.3 Endpoints

2.3.1 **Primary Endpoint**

 The primary efficacy endpoint of the study is clinical ruxolitinib response of quantitative ΔTumor size measured as a proportional percent (range -100% to +100%) from baseline to day 14-21.

Phase 2 - Ruxolitinib Page 23 of 67

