8.2 Determination of Sample Size and Accrual Rate

8.2.1 Sample Size and Power Estimate

The primary objective of the study is to identify baseline and/or pharmacodynamic biomarkers that might have predictive utility to determine the clinical response to ruxolitinib. As a biomarker study, the statistical design is to accrue a sufficient number of patients and provide 80% power to test one or any of 5 key hypotheses with a shared alpha of 0.15: 1) relationship between clinical response (ΔTumor size) and baseline STAT activation (pSTAT3 expression); 2) relationship between clinical response (ΔTumor size) and change in expression of pSTAT3; 3) relationship between responders (ΔTumor size) and change in expression of cyclin D1: 4) relationship between clinical response (ΔTumor size) and baseline genetic or epigenetic PTPRT or PTPRD silencing; 5) relationship between responders (ΔTumor size) and baseline C-reactive protein. An overall alpha of .15 will be shared equally among the five primary hypotheses. 23 patients with complete biomarker data are needed to achieve 80% power for the 5 primary hypothesis and limit overall family wise error rate (FWER) to 15%. As estimated from our prior window trials, accounting for treatment compliance and quality paired tumor specimens, this will require enrollment of 45 patients. For each biomarker (baseline pSTAT3 expression, change from baseline of pSTAT3 expression, change from baseline of cycline D1 expression, baseline PTPRT or PTPRD silencing and baseline C-reactive protein), mean and standard deviation will be estimated and compared for significance between clinical responders and non-responders of ruxolitinib therapy using Wilcoxon rank tests. Our experience with our phase 0 clinical trial testing the STAT3 decoy also showed correlations between ΔKi-67 (the primary pharmacodynamic efficacy endpoint) and STAT3-target genes falling in the range of .50 to .67. Twenty-five patients will enable a two -tailed Spearman Correlation test at alpha = .03 to detect a true correlation of .56. For the expected 30% of patients with a PTPR mutation, a one-tailed Wilcoxon test will demonstrate increased sensitivity to ruxolitinib via a decrease in tumor size equal to 1.3 standard deviations with 23 patients (8 with a mutation).

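### The 80% power in 8.2.1 does not match the Spearman test at 23 patients or the marker defined for hypothesis 4, and 8.4.1 and 8.2.1 retain responder wording that conflicts with 8.4.2

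*Combined protocol and SAP*

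**What the plan says.** **Endpoint and primary test.** Section 2.1 hypothesises that "ΔTumor size will correlate with five prioritized, predictive biomarkers which will be designated for specialized alpha spending". Section 2.3.1 defines the primary endpoint as "quantitative ΔTumor size measured as a proportional percent (range -100% to +100%) from baseline to day 14-21". Section 8.4.2 names Spearman correlation with percent change as the primary analysis for each of the five markers, and ranks the Wilcoxon comparison at a 35% reduction as supportive and exploratory.

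**Text that differs.** Section 8.4.1 (Efficacy Population) reads "The efficacy population for the primary endpoint of 35% or greater reduction in tumor size will include all enrolled patients". Section 8.2.1 says each marker will be "compared for significance between clinical responders and non-responders of ruxolitinib therapy using Wilcoxon rank tests", with no cut-off and no exploratory label, and it words hypotheses 3 and 5 in terms of responders.

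**Power.** Section 8.2.1 shares an overall alpha of .15 equally among the five hypotheses and states that "23 patients with complete biomarker data are needed to achieve 80% power for the 5 primary hypothesis". The supporting Spearman sentence reads "Twenty-five patients will enable a two -tailed Spearman Correlation test at alpha = .03 to detect a true correlation of .56". It follows a sentence giving correlations of .50 to .67 between STAT3 target genes and ΔKi-67. For hypothesis 4, 8.2.1 says "For the expected 30% of patients with a PTPR mutation, a one-tailed Wilcoxon test will demonstrate increased sensitivity to ruxolitinib", for a difference of 1.3 SD with 8 mutated patients among 23. Section 2.1 defines that marker as "baseline silencing of protein tyrosine phosphatase receptors D or T (PTPRD or PTPRT) by mutation or methylation", and 8.4.2(4) likewise analyses genetic or epigenetic silencing.

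**The concern.** The test that is sized and the test that will be run should be the same, with the same number of patients, marker and direction. Here the headline number (23) differs from the number in the Spearman calculation (25). The hypothesis 4 calculation uses a narrower marker than the one to be analysed, and a one-tailed test where 8.4.2 gives no direction. If the stated 80% is too high, a null result would be read as stronger evidence against a biomarker than it is.

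The responder wording raises a second question: which endpoint is primary, and which test spends the alpha. In an open-label study with five markers, the document should give one answer everywhere.

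**Working it through.** **Alpha.** .15 / 5 = .03 per hypothesis. This matches the Spearman sentence. Critical values: z(.985) = 2.170 two-sided, z(.97) = 1.881 one-sided.

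**Spearman power.** Power = Φ(atanh(ρ)·√((n − 3)/c) − 2.170), with atanh(.56) = .6328. The constant c is 1 (plain Fisher z), 1.06, or 1 + ρ²/2 = 1.157 (two common adjustments for Spearman).

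The plan's own sentence first, n = 25, c = 1: .6328 × √22 = 2.968; 2.968 − 2.170 = .798; Φ = .788. That is close to 80%, so the sentence is sound at its own number.

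The same at n = 23: .6328 × √20 = 2.830; 2.830 − 2.170 = .660; Φ = .745.

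| Method, ρ = .56, two-sided .03 | n = 23 | n = 25 |
|---|---|---|
| c = 1 | .745 | .788 |
| c = 1.06 | .719 | .762 |
| c = 1.157 | .678 | .722 |
| Simulation, .56 as Pearson | .69 | .73 |
| Simulation, .56 as Spearman | .73 | .77 |

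The simulations are bivariate normal, 100,000 data sets per cell, with the t approximation for Spearman.

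Correlation needed for 80% at n = 23: tanh((2.170 + .842)·√(c/20)) = .587 for c = 1 and .600 for c = 1.06. Simulation needs a Pearson correlation of about .615, which is a Spearman correlation of about .60. The most conservative variance gives .63.

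**Hypothesis 4.** Normal shift of 1.3 SD, 23 patients, alpha .03, 200,000 simulated data sets per split. With a two-level marker, Spearman and Wilcoxon rank the data identically and differ only in the reference distribution. Each range below therefore runs from exact Wilcoxon to Spearman with the t approximation.

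Expected silenced share, from section 1.3: 30% mutated, 60% with PTPRT methylation.
- Full overlap: max(.30, .60) = .60; × 23 = 13.8, about 14 vs 9.
- Independence: 1 − .70 × .40 = .72; × 23 = 16.6, about 17 vs 6.

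| Split | Basis | One-tailed | Two-sided |
|---|---|---|---|
| 8 vs 15 | as stated, mutation only | .80–.82 | .70–.73 |
| 14 vs 9 | full overlap | .81–.83 | .72–.75 |
| 17 vs 6 | independence | .72–.75 | about .62 |

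The first row reproduces the plan's figure one-tailed. PTPRD methylation is not given, so 60% is a floor under these inputs.

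**Endpoint wording.** Sections 2.1, 2.3.1 and 8.4.2 agree with one another. The 8.4.1 label and the responder sentence in 8.2.1 do not agree with them. The membership rule in 8.4.1 (measurable disease at baseline and a completed assessment at the end of the window) is the same whether the endpoint is continuous or binary.

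**The case against.** **The 80% may not be per hypothesis.** Section 8.2.1 also speaks of power to test one or any of the five. On an at-least-one reading with 23 patients, a correlation of .56 and markers independent given tumor change, simulation gives .73–.76 if one marker is truly correlated, .90–.92 if two are, and .99 if all five are. So 80% could hold. This stands, and it is why the plan must say which reading is meant.

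**The gap is small, and .56 is not the only correlation given.** The range .50–.67 is also quoted, and about .59–.60 gives 80% at 23 on the usual formulas. That stands too, but the plan does not name that effect. Both figures sit in a passage about ΔKi-67, so using them for ΔTumor size is an assumption.

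**Hypothesis 4 can still reach 80%.** At 14 vs 9 a one-tailed test does. The shortfall depends on the direction and on how far mutation and methylation overlap. Two-level coding is also assumed, since 8.4.2(4) plans a mean and SD for silencing. A reader might infer a collapse in power by assuming that the two never coincide (90% silenced); nothing in the documents suggests that, so it is not relied on.

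**The endpoint conflict is already resolved in 8.4.2.** Largely so. A reader might infer that the 35% test competes for alpha, with inflated family-wise error or a very weak primary test. That follows only if 8.4.2 is ignored, and the documents give no responder rate from which to size it.

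**Conclusion.** The point holds as a mismatch between the stated power and the planned analysis.

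- **Spearman:** read per hypothesis, 23 patients give about 68–75% power at the correlation of .56, not 80%. About .59–.62 would be needed for 80%. This assumes near-normal data and that .56 applies to ΔTumor size.
- **Hypothesis 4:** the arithmetic is right for mutation alone but describes a different marker. For mutation or methylation, one-tailed power is 81–83% at 14 vs 9 and 72–75% at 17 vs 6; two-sided it is 72–75% and about 62%. The splits rest on the protocol's 30% and 60% and on the assumed overlap.
- **Endpoint:** the label in 8.4.1 and the responder test in 8.2.1 are wording to be corrected. The documents do not support a claim that the primary analysis is undefined.

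It should be fixed. Confidence is high on the textual mismatches. The size of any power loss depends on the assumptions above.

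**What to change.** **8.2.1, Spearman.** State the power for 23 patients: roughly 70–75% at .56 by most methods, or 80% at about .59–.62. Say that .56 is an assumption for ΔTumor size, and whether 80% is meant per hypothesis or for at least one of five.

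**8.2.1, hypothesis 4.** Base the statement on silencing by mutation or methylation, with the expected silenced share. Choose one sidedness and state it in both 8.2.1 and 8.4.2(4).

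**8.4.1.** Name the primary endpoint as percent change in tumor size from baseline, in place of the 35% label.

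**8.2.1, responder wording.** Mark the responder Wilcoxon as exploratory with no alpha, and reword hypotheses 3 and 5 in terms of percent change in tumor size.

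**Cost.** Text only, with no new visits or data; the stated power becomes less favourable. Enlarging the study is optional. By the three formulas above, 80% at .56 needs 26 to 30 evaluable patients, which at the plan's own yield is 26 × 45/23 ≈ 51 to 30 × 45/23 ≈ 59 enrolled.
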